**Study Comprehension:**

Responses to the U54 Study Booklet questionnaire will be summarized by frequency counts and percentages to each question asked. Improvement to the study booklet will be categorized by type of improvement suggested and summarized by frequency counts and percentages.

**Background and Demographic Characteristics:** Background and demographic characteristics will be listed by participant. Continuous variables will be summarized by sample size (n), mean, median, standard deviation (SD),

minimum, and maximum. Discrete variables will be summarized by frequencies and percentages.

**Concomitant Therapy:** Descriptive statistics such as frequency counts and percentages of participants who use concomitant medications will be provided by therapeutic classification and specific therapy.

## 20.2 Sample Size Determination

We hypothesize that there are at least two discrete ATX response phenotypes groups and additionally that these groups may be distinguished by differences in pharmacodynamic markers, and/or baseline patient characteristics. We will use two-sample *t*-tests (if transformed data are approximately Gaussian) or appropriate non-parametric alternatives to test for group differences in baseline and maximal change in DHPG, and a difference in proportions test to assess association between response group and SLC6A2 genotype. To estimate power for these tests we assumed 20% attrition and simulated data for 96 patients. For a 30% response rate among study completers (a conservative estimate),  $\alpha = 0.05$ , and power = 80%, a mean difference of 0.6 SDs between responders and non-responders (eg, on DHPG) was detectable using a one-sided *t*-test. With 120 patients (zero attrition) a 0.5 SD difference was detectable. Depending on the rate and nature of attrition and missing data we will consider non-response weighting or data imputation to reduce estimation bias and improve power. We assessed power for the difference in proportions test based on a 45% probability of a given patient having at least one SLC6A2 lower expression “T” allele (*i.e.*, frequency of SLC6A2 -3081 AT and TT genotypes ~45% based on a minor T allele frequency of 0.061

([http://useast.ensembl.org/Homo\\_sapiens/Variation/Population?db=core;g=ENS G00000103546;r=16:55655604-55706192;v=rs28386840;vdb=variation;vf=109832868](http://useast.ensembl.org/Homo_sapiens/Variation/Population?db=core;g=ENS G00000103546;r=16:55655604-55706192;v=rs28386840;vdb=variation;vf=109832868))).

Assuming attrition of 20% and a response rate of 30%, power was 81% to detect a 0.23 difference in allele frequency between responders and non-responders using a one-sided test. With 120 patients a 0.20 difference was detectable with 80% power.

While these analyses are central to our hypothesis, we recognize that other plasma metabolites or genetic differences may contribute to varying drug response. A target metabolite panel will be assayed in each participant and statistical analyses of these will be analogous to DHPG. A panel of genetic variants will also be analyzed for contribution to variable drug pharmacokinetics, pharmacodynamics, and clinical response in the same manner as the SLC6A2 variant described above.

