The *CYP2D6* gene, which encodes for the drug metabolizing enzyme CYP2D6 responsible for the clearance of ATX from the body, is highly polymorphic (Gaedigk et al., 2007; Gaedigk et al., 2010; Gaedigk et al., 2010; Gaedigk, 2013). ATX metabolism by CYP2D6 protein is one of the major routes of clearance (i.e., removal) of this drug. Genetic variability in the *CYP2D6* gene leads to wide inter-individual variability in the activity of the enzyme, ultimately resulting in differing amount of drug in the body (also referred to as “exposure,” and is a component of drug pharmacokinetics). Secondly, the *SLC6A2* gene which encodes for the norepinephrine reuptake transporter, the drug target for ATX, is also subject to genetic variation. Reported genetic variants of *SLC6A2* have been associated with decreased abundance of the transporter (Kim et al., 2006). The consequences of *SLC6A2* genetic variation with regards to ATX clinical response are currently unknown. In the context of distinct “responder” and “non-responder” groups with a population of atomoxetine-treated patients, non-response could be due to definable differences at the level of the drug target (patients unlikely to respond regardless of the ATX concentrations achieved), or simply a consequence of inadequate exposure in a substantial proportion of population. The goal of this study is to address this issue.

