Variables that will be included in this analysis are data collected at the patient's initial clinic visit: DHPG, *SLC6A2* genotype, ADHD subtype, ADHD severity, co-morbid anxiety or oppositional defiant disorder, age, and gender. Predictive power of classification models will be assessed by computing the area under the receiver operating characteristic curve and/or by k-fold cross-validation. Two-sample t-tests or non-parametric alternatives will be utilized to test for group differences in percent decrease in DHPG and a differences in proportions test will be used to assess the association between response and *SLC6A2* genotype. In addition, global metabolomic analyses will be conducted to determine whether non-responders and responders are intrinsically different in their biochemical make-up. This will further understanding of how differences in

response phenotype could be a result of different biological pathway involvement in ADHD. Digital maps will be constructed for partial least square-discriminant analysis (PLS-DA) models with prior knowledge of which volunteers were categorized as responders and non-responders. The variable influence on the projection (VIP) parameter will be used to identify which metabolites (i.e. pathways) are the most predictive of differentiating between the responder and non-responder populations. Analyses will also be conducted to determine mechanistic reasons for why certain individuals are non-responders or responders. Changes in pharmacodynamic endpoints will be compared between responders and non-responders. Specifically pharmacodynamic parameters such as  $I_{max}$ ,  $IC_{50}$ , differences in pupil diameter changes in localizations and discrimination tasks, and overall change in DHPG will be compared between the two populations using MANOVA and/or appropriate two-sample test.

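### The SLC6A2 power statement uses two inputs that contradict each other: a T allele frequency of 0.061 gives about 12% carriers, not 45%, and on 45% the power is about 67% and 65%, not 81% and 80%

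*Combined protocol and SAP*

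**What the plan says.** Section 20.2 (Sample Size Determination) plans a difference-in-proportions test of response group against SLC6A2 genotype. Section 20.1 repeats it: "a differences in proportions test will be used to assess the association between response and" SLC6A2 genotype. Section 20.2 gives the basis for power as follows:

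- Power was assessed "based on a 45% probability of a given patient having at least one SLC6A2 lower expression" allele.
- The source of the 45% is given as "frequency of SLC6A2 -3081 AT and TT genotypes ~45% based on a minor T allele frequency of 0.061".
- With 20% attrition (96 patients) and a 30% response rate, "power was 81% to detect a 0.23 difference in allele frequency between responders and non-responders using a one-sided test".
- For the case of no attrition, the section adds a second figure: "With 120 patients a 0.20 difference was detectable with 80% power".

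Section 20.2 describes these analyses as central to the hypothesis, and says other genetic variants will be handled in the same way.

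**The concern.** The carrier rate and the allele frequency appear in one parenthesis, one as the source of the other, and they differ by nearly a factor of four. Power for a difference in proportions depends on where the proportions lie, so the choice between about 12% and 45% decides whether the printed 81% and 80% are right.

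This is the plan's only power statement for the genotype test. The carrier rate also sets the size of the genotype groups. If carriers are compared with non-carriers, the groups would be about 43 vs 53 children at 45%, and about 11 vs 85 at 12%.

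Two further points are left open. The 45% is a per-patient probability, but the effect is called a difference in allele frequency. The test is one-sided with no direction given, although section 3.1 says the consequences of SLC6A2 "genetic variation with regards to ATX clinical response are currently unknown".

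**Working it through.** **Inputs.** From section 20.2: N = 96 or 120, 30% responders, one-sided test, carrier probability 45%, T frequency 0.061, differences 0.23 and 0.20. The α of 0.05 is stated there for the t-test and in section 20.1 for the analyses generally. Group sizes are 0.30 × 96 = 28.8, taken as 29 vs 67, and 0.30 × 120 = 36 vs 84.

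**Step 1: carrier rate.** Under Hardy-Weinberg, carriers = 1 − (1 − q)².

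- q = 0.061 gives 1 − 0.939² = 0.118. Under any genotype distribution the limit is 2 × 0.061 = 0.122.
- For 45% carriers, q = 1 − √0.55 = 0.258.

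**Step 2: power formula.** One-sided z-test with pooled null variance, R = responders, N = non-responders:

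power = Φ[(|p_R − p_N| − 1.645·s₀)/s₁], where s₀ = √[p̄(1 − p̄)(1/n_R + 1/n_N)] and s₁ = √[p_R(1 − p_R)/n_R + p_N(1 − p_N)/n_N].

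**Step 3: recovering the printed figures.** Take 11.8% as the non-responder rate, with responders higher.

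- 96 patients: p_N = 0.118, p_R = 0.348, s₀ = 0.0868, s₁ = 0.0969. (0.23 − 0.1428)/0.0969 = 0.90, so power is 81.6% (printed: 81%).
- 120 patients: p_N = 0.118, p_R = 0.318, s₀ = 0.0762, s₁ = 0.0853. (0.20 − 0.1254)/0.0853 = 0.875, so power is 80.9% (printed: 80%).

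**Step 4: power on the 45% that the text names.** Take 45% as the overall rate, with responders higher.

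- 96 patients: p_N = 0.45 − (29/96)(0.23) = 0.381, p_R = 0.611, s₀ = 0.1106, s₁ = 0.1082. (0.23 − 0.1819)/0.1082 = 0.444, so power is 67.2% (exact binomial 67.8%).
- 120 patients: p_N = 0.390, p_R = 0.590, s₀ = 0.0991, s₁ = 0.0977. (0.20 − 0.1630)/0.0977 = 0.379, so power is 64.7% (exact binomial 64.5%).

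**Step 5: other placements of the carrier rate (pooled formula).**

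| Carrier rate and where it applies | N = 96, diff 0.23 | N = 120, diff 0.20 |
|---|---|---|
| 45% overall, responders higher | 67.2% | 64.7% |
| 45% overall, responders lower | 67.8% | 65.2% |
| 45% in non-responders, responders higher | 67.3% | 64.7% |
| 45% in non-responders, responders lower | 70.4% | 67.2% |
| 45% in responders, non-responders lower | 72.9% | 69.4% |
| 45% in responders, non-responders higher | 68.3% | 65.4% |
| 11.8% in non-responders, responders higher | 81.6% | 80.9% |
| 11.8% overall, responders higher | 90.0% | 88.8% |
| 11.8% in responders, non-responders higher | 78.5% | 77.8% |
| Plan | 81% | 80% |

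Other variance formulas without continuity correction reach at most 76% and 72% on the 45%. Fisher's test gives about 60% and 57%.

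**Step 6: detectable difference at 80% power.** With 45% overall, 0.272 (N = 96) and 0.244 (N = 120). With 11.8% in non-responders, 0.223 and 0.197.

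**Step 7: carriers expected.** At 11.8%, 96 × 0.118 = 11.4 and 120 × 0.118 = 14.2. Under the 0.23 alternative, 29 × 0.348 + 67 × 0.118 = 18.0. At 45%, 96 × 0.45 = 43.2.

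**Step 8: unit and direction.** Counting two alleles per child (58 vs 134 and 72 vs 168), with responders higher, gives 92.4% and 91.3% for T = 0.258 in non-responders, and 98.8% for both sample sizes for T = 0.061. With 11.8% in non-responders, a drop of 0.20 or 0.23 would make the responder rate negative, so the alternative can only be that responders carry T more often.

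**The case against.** The strongest reply is that the test of association can be set up from the other margin: response rate in carriers against non-carriers. With 45% carriers (43 vs 53, and 54 vs 66) and 30% response overall, the pooled formula gives 80.2% and 77.9% if carriers respond less, and 79.1% and 77.0% if they respond more. That comes close to the printed figures while keeping the 45%, so the fault could be a mislabelled effect and not overstated power. This cannot be excluded. However, section 20.2 defines the difference as lying between responders and non-responders, and this margin fits the printed pair less closely than 11.8% in non-responders does.

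A second reply is that 0.061 may be a misprint. A frequency of 0.261 would give 1 − 0.739² = 45.4%. That is plausible but is an inference, since the cited database is not available here. It would remove the small carrier group but leave the power at about 67% and 65% on the reading the text gives.

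It is also fair that 67% and 65% depend on the reference group and test formula, which the plan leaves open, and that section 20.1 does not define its genotype groups. The sample size was set by patient volume, so it does not rest on this calculation. None of this reconciles 0.061 with 45%.

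**Conclusion.** The concern holds. The contradiction between 0.061 and 45% is certain and needs no outside source. Read as written (a carrier difference between response groups, 45% carriers, 30% responders, one-sided 5%), power is about 67% and 65%, some 14 to 15 points below the plan. Across placements of the 45% it is 67–73% and 65–69%. If 0.061 is right, the printed powers roughly stand (82% and 81%), but only with 11.8% as the non-responder rate and responders higher, and with about 11 carriers among 96 children at the population rate. The documents do not show which input was used. The figures assume the pooled z-test, and the 11.8% carrier rate assumes Hardy-Weinberg proportions.

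**What to change.** Check the T allele frequency against the cited source and correct whichever input is wrong. In section 20.2, state the carrier rate and the group it applies to, whether the unit is carriers or alleles, and the direction of the one-sided test. Then restate the power:

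- **If 45% is right:** correct the allele frequency (about 0.26). With 45% as the overall rate, give about 67% power for a 0.23 difference in carrier proportion with 96 patients and about 65% for 0.20 with 120. The differences detectable at 80% power are about 0.27 and 0.245.
- **If 0.061 is right:** replace 45% with about 12%. Give power on that basis (about 82% and 81% with 12% in non-responders and responders higher), and acknowledge carrier groups of about 11 vs 85.
- **If the difference was meant as one in response rate between carriers and non-carriers:** say so, and recompute on the corrected carrier rate.

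The cost is one source check and a rewritten paragraph. Under the first outcome the stated power becomes less favourable. Under the second the carrier group shrinks. The sample size need not change, because section 20.1 justifies 120 by referral volume.

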### 20.3 Confidentiality

Research records which include, but are not limited to: participant study binders, financial binders, regulatory binders, study logs, etc. These records will be stored in a locked cabinet in the study coordinators' office or will be stored on Children's Mercy Hospital secure server. Any electronic files containing PHI will be password protected. Access to research records and data will be restricted to study personnel and project collaborators. Information shared with project collaborators will be on a need to know basis and will be limited to the information needed to perform thorough data analysis. Study personnel who will be in contact with PHI will be trained on PHI practices in accordance to Children's Mercy Hospital standards and will regularly be certified per institution policy.

### 20.4 Certificate of Confidentiality

A Certificate of Confidentiality has not been issued for this investigation. The original notice of award for this grant (Funding ID: 1-U54-HD090258-01) was issued on 09/23/2016, which is prior to the date when Certificates of Confidentiality were automatically supplied by the National Institutes of Health.

### 20.5 Quality Control and Assurance

Quality Control (QC) and Quality Assurance (QA) of data collected as a part of this investigation will be described in a Clinical Quality Management Plan (CQMP) (Supplementary Documents, "Clinical Quality Management Plan."). Under this plan, QA and QC procedures will take place at each subject study visit and on a quarterly and annual schedule, and as needed in response to staff or process changes. Key components reviewed in these processes will include: consent and permission/assent processes and documentation, review of participant-related CRFs, review of study drug accountability logs, review and update of the delegation of authority, review and update of the training log, and review and update of the regulatory binder. Documentation of all QC and QA processes outlined in the CQMP except for visit checklists will be maintained in the Quality Management Binder alongside the study regulatory binders. Visit checklists will be maintained in the study subject binder.

### 20.6 Data and Sample Handling

All samples will be stored within the Clinical Pharmacology laboratories under appropriate storage conditions. Access to the laboratory is secured by card access only. Samples will be associated with a study identification number: U54-XYZ (where XYZ denotes a number assigned by study personnel). Samples will be stored and kept until such time that all samples have been processed, data are

finalized, and manuscripts/publications detailing study findings have been completed. All research personnel, research associates, and laboratory staff will have access to samples and research data. Sample information may be shared with associates of study personnel (e.g. grant collaborators) for the purposes of data analysis that are relevant to achieving study objectives and aims detailed in the grant funding this project (1-U54-HD090258-01).

Receipt and transmission of data and/or samples will be conducted by study personnel designated in the Delegation of Authority Log. Samples that need to be transported or transferred to a facility outside of Children's Mercy Hospital will be shipped overnight on dry ice, following the Children's Mercy Hospital's Policy, 1200.RLSM Transport of Research Materials Ver1.2.

## **21.0 Provisions to Monitor the Data to Ensure the Safety of Subjects**

### **21.1 Data Safety Monitoring Board**

The PI and study personnel will be responsible for monitoring the safety of participants. Additionally, a Data and Safety Monitoring Board (DSMB) will be organized to review the progress of the study and ensure the safety of study participants per Children's Mercy Hospital Policy 11.01 Data Safety Monitoring. The board will consist of faculty from both the Children's Mercy Hospital, national experts on clinical pharmacology, and physicians who have previously or are actively involved in the care of children with ADHD. The board will consist of:

- [name], PhD
- [name], PhD
- [name], DO
- [name], MS

[name] and [name] are child psychiatrists at UCLA Mattel Children's Hospital and Resnick Neuropsychiatric Hospital at UCLA. [name] is a child psychiatrist at Children's Mercy Hospital. [name] is an infectious disease physician with expertise in adverse drug reactions.

The board will meet on a bi-annual basis and after all participants have been enrolled and completed study procedures. Further ad-hoc meetings will be determined by the PI and DSMB, particularly in the event of new or significant findings. Documentation of the meetings will be recorded and stored in the Division of Clinical Pharmacology, Toxicology & Therapeutic Innovation at Children's Mercy Hospital and Clinics and will be submitted to myIRB. The DSMB will be responsible for monitoring adverse events, serious adverse events,

enrollment numbers, protocol violations/deviations, participant withdrawal(s)/termination(s), and efficacy data.

**Collection of Safety Information:**

Safety information will include source documents that record measures to reduce risk for participants (section 11.3), QC/QA findings reports (section 20.5), and adverse events (section 4.2).

Please Supplementary Documents, “DSMB Charter,” and “DSMB Protocol” for further details.

## **22.0 Provisions to Protect the Privacy Interests of Subjects**

### **22.1 Privacy Interest**

The study will follow standards established by the following Children’s Mercy Hospital policy: Request Restrictions to Protected Health Information.

### **22.2 At Ease**

The study team will allow the participant and their families time to decide whether he/she wants to both participate and continue in the study. Families are given at least a week to review the permission/assent forms before deciding whether to participate in this study. During enrollment, families are encouraged to ask questions and additionally, a supplemental illustrated booklet detailing study procedures is provided to the family. The study team will review the type of information that is being collected with the participant and their family. The participant and their family will also be asked at each research visit whether they would like to continue to participate in the study.

### **22.3 Permission to Access Data**

The study will follow standards established by the following Children’s Mercy Hospital policies: Confidentiality; HIPAA & Privacy Manual Standard.

### **22.4 PHI to be Accessed**

The electronic medical record will be accessed for the purposes of recruitment and prescreening (see section 9.0). Data related to ADHD and comorbidity symptoms will be collected from the participant EMR for the purposes of data analysis.

#### 22.5 HIPAA Authorization

The study has a partial HIPAA waiver for the purposes of recruitment and prescreening (see section 9.0).

### **23.0 Compensation for Research-Related Injury**

There is no compensation for research-related injury. Should illness or injury occur during participation in this study, treatment is available and will be provided at the usual charge. Payment for this treatment will be the responsibility of the participant.

### **24.0 Economic Burden to Subjects**

Participation in Research Visit 1, Research Visit 2, Research Visit 3, and Research Visit 4 will not result in any extra cost to the participant or their parents aside from personal time and travel costs to come to these visits.

Intake Visit with Study Physician, 6-Week Visit with Study Physician Visit, 12-Week Visit with Study Physician, and 18-Week with Study Physician may incur extra costs to the participant or their families depending on their insurance plan. This is because the Study Physicians involved in the care of the participants are considered consultants and these visits with the Study Physician may be considered as referrals to secondary care.

### **25.0 Permission/Assent/Consent Process**

The research team will be obtaining permission and assent if the potential participant is younger than 18 years of age. Consent will be obtained if the potential participant is over 18 years of age and if the participant turns 18 during the study.

- Permission/assent or consent may be conducted in person with the study team at the PCRU or this may take place over the phone.
- The research team will wait at least for at least a period of one week between informing the prospective subject and obtaining either permission/assent or consent.
- Permission and assent will be reaffirmed prior to any research procedures take place at Research Visit 1, Research Visit 2, Research Visit 3, and Research Visit 4.
- This research study will be following the CM research policies regarding informed permission/assent/consent.
- This research team will be obtaining permission/assent/consent via telephone, and we will be following CM research policy 10.05 Telephone Process regarding telephone consent.

- The permission/assent and consent forms will contain a section for participants to allow their data and samples to be stored in the PK/PD Repository for use in prospective research.

